8.2.9 Outcome of Adverse Events

The outcome of each reportable adverse event will be classified by the investigator as follows:

- RECOVERED/RESOLVED – The participant recovered from the AE/SAE without sequelae. Record the AE/SAE stop date.
- RECOVERED/RESOLVED WITH SEQUELAE – The event persisted and had stabilized without change in the event anticipated. Record the AE/SAE stop date.
- FATAL – A fatal outcome is defined as the SAE that resulted in death. Only the event that was the cause of death should be reported as fatal. AEs/SAEs that were ongoing at the time of death; however, were not the cause of death, will be recorded as “resolved” at the time of death.
- NOT RECOVERED/NOT RESOLVED (ONGOING) – An ongoing AE/SAE is defined as the event was ongoing with an undetermined outcome.
 - An ongoing outcome will require follow-up by the site in order to determine the final outcome of the AE/SAE.
 - The outcome of an ongoing event at the time of death that was not the cause of death, will be updated and recorded as “resolved” with the date of death recorded as the stop date.
- UNKNOWN – An unknown outcome is defined as an inability to access the participant or the participant’s records to determine the outcome (for example, a participant that was lost to follow-up).

If any reported adverse events are ongoing when a participant completes the study (or withdraws), adverse events classified UADEs will be followed until they are either resolved, or have no prospect of improvement or change, even after the participant has completed all applicable study visits/contacts. For all other adverse events, data collection will end at the time the participant completes the study. Note: participants should continue to receive appropriate medical care for an adverse event after their participation in the study ends.

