2. EKG
For Cohort A, an EKG will be performed at Screening and at the 6, 26, and 52 week visits. The screening EKG must be read by a pediatric cardiologist to ensure there is no underlying abnormality that precludes study participation. The automated reading will be acceptable if normal for subsequent EKGs. Any automated EKG readings suggesting abnormalities in QTc and/or PR intervals will be referred to a pediatric cardiologist for interpretation.
3. Liver function tests
For Cohort A, AST/ALT will be measured locally at Screening and at the 6, 26, and 52 week visits
4. Kidney tests
For Cohort A, creatinine will be measured locally at Screening and used to calculate eGFR
5. Urine or serum pregnancy:
Performed locally for females with childbearing potential at Screening and each follow up visit, and also anytime pregnancy is suspected. Must be negative to perform the MMTT.
6. MMTT:
2-hour MMTT for stimulated glucose and C-peptide will be done at Randomization, 13, 26, 39, and 52 week visits, with samples collected at 0, 15, 30, 60, 90 and 120 minutes. Criteria will be detailed in the site procedures manual.

903 7. HbA1c:
904 Collected for central lab analysis at Randomization, 13, 26, 39, and 52 week visits
905 8. Measures of beta cell health and immune function:
906 Blood/serum/plasma will be drawn and sent to the appropriate lab, to assess several
907 measures detailed below. Samples at some of the time points may or may not be run
908 depending on final study results.

909 i. Pro-insulin and Pro-IAPP and their ratios to C-peptide during the MMTT at 0 and
910 90 minutes, collected at Randomization, 13, 26, 39, and 52 week visits
911 ii. Circulating unmethylated INS DNA, collected at Randomization, 13, 26, 39, and
912 52 week visits
913 iii. Circulating plasma miRNA sequencing, collected at Randomization, 13, 26, 39,
914 and 52 week visits
915 iv. T-cell characteristics by PBMC and peripheral cytokine levels, collected at
916 Randomization, 26 and 52 week visits only.
917 v. Collection and storage of extra samples of plasma as blood volume limitations for
918 size allow and/or storage of any remaining samples for future research, collected at
919 Randomization, 26, and 52 week visits only, as approved by the participants.

920
921 *Local laboratory testing will be performed if needed to screen for exclusionary medical*
922 *conditions.*

Chapter 8: Unanticipated Problems, Adverse Events, Device Issues, and Stopping Rules

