8.2 Adverse Events

8.2.1 Definitions

Adverse Event (AE): Any untoward medical occurrence in a study participant, irrespective of the relationship between the adverse event and the drug/device(s) under investigation (see Section 8.2.2 for reportable adverse events for this protocol).

Serious Adverse Event (SAE): Any untoward medical occurrence that:

- Results in death.
- Is life-threatening; (a non-life-threatening event which, had it been more severe, might have become life-threatening, is not necessarily considered a serious adverse event).
- Requires inpatient hospitalization or prolongation of existing hospitalization.
- Results in persistent or significant disability/incapacity or substantial disruption of the ability to conduct normal life functions (sight threatening).
- Is a congenital anomaly or birth defect.

962 • Is considered a significant medical event by the investigator based on medical judgment
963 (e.g., may jeopardize the participant or may require medical/surgical intervention to
964 prevent one of the outcomes listed above).

965
966 Unanticipated Adverse Device Effect (UADE): Any serious adverse effect on health or safety or
967 any life-threatening problem or death caused by, or associated with, a device, if that effect,
968 problem, or death was not previously identified in nature, severity, or degree of incidence in the
969 package insert, this protocol, or the informed consent document, or any other unanticipated
970 serious problem associated with a device that relates to the rights, safety, or welfare of
971 participants (21 CFR 812.3(s)).

972
973 Adverse Device Effect (ADE): Any untoward medical occurrence in a study participant which
974 the device may have caused or to which the device may have contributed (Note that an Adverse
975 Event Form is to be completed in addition to a Device Deficiency or Issue Form, unless excluded
976 from reporting as defined in Sections 8.2.2-8.2.4). *An event that occurs solely due to participant
977 (i.e., user) error in which the device functions properly generally will not be considered an ADE
978 unless it is determined that the instructions on the screen of the device or user manual (or
979 similar training materials) may have contributed to the event (note: the event may still meet
980 criteria for reporting as an adverse event).*

981
982 Device Complaints and Malfunctions: A device complication or complaint is something that

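### Section 8.2.9 follows events still open at study completion only if they are device effects, so the final outcome of a drug-related SAE, or of an EKG or AST/ALT adverse event, open at week 52 is generally not collected

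*Protocol*

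**What the plan says.** Protocol Section 8.2.9 contains two statements on unresolved events.

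- Under the outcome code for unresolved events: "An ongoing AE/SAE is defined as the event was ongoing with an undetermined outcome". It adds: "An ongoing outcome will require follow-up by the site in order to determine the final outcome of the AE/SAE". No time limit is given.
- In the closing paragraph, for events ongoing when a participant completes or withdraws: "adverse events classified UADEs will be followed until they are either resolved, or have no prospect of improvement or change", even after all visits and contacts are done. Then: "For all other adverse events, data collection will end at the time the participant completes the study". The next sentence notes that "participants should continue to receive appropriate medical care for an adverse event after their participation in the study ends".

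Section 8.2.1 defines a UADE as a serious effect on health or safety, or "any life-threatening problem or death caused by, or associated with, a device, if that effect" was not already identified in the package insert, protocol or consent document. A further limb covers other unanticipated serious problems, again associated with a device.

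On drug safety testing, Section 7.2 says: "For Cohort A, an EKG will be performed at Screening and at the 6, 26, and 52 week visits", and "For Cohort A, AST/ALT will be measured locally at Screening and at the 6, 26, and 52 week visits". Section 6.1 keeps participants on the study interventions until the final visit is completed, even if it is late.

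**The concern.** The trial tests a drug as well as devices, yet the rule for following events past the end of the study is written for devices alone. Section 1.2.1 names EKG changes (including QTc and PR intervals) and AST/ALT changes as matters to monitor in patients on verapamil, and Section 1.3 states that the drug is used off-label. The final scheduled tests for these effects fall on the last day of participation, and the closing paragraph of 8.2.9 then stops data collection on whatever they show.

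What is at stake is one kind of evidence. Section 8.2.5 lists abatement after stopping the drug, or reducing its dose, among the grounds for calling an event related. For an event open at week 52, the planned end of treatment is that stop, and the study does not record what happens next. The two statements in 8.2.9 also leave sites room to act differently: one asks for follow-up to a final outcome without limit, the other stops it for most events.

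**Working it through.** The plan states no figure on this point. The check sets the provisions side by side, then sizes the group concerned.

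**1. Which events continue to be followed.** 8.2.9 names UADEs only. By 8.2.1 these are tied to a device. An SAE attributed to study drug alone is therefore outside the rule however serious it is, and so is a non-serious EKG or AST/ALT adverse event.

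**2. Whether such events can be open at the end.** Section 8.2.2 counts findings from laboratory or other tests as reportable if they meet the adverse event definition. After screening, Cohort A is tested at week 6 (timed from randomization) and at weeks 26 and 52 (timed from diagnosis). An abnormality first seen at week 52 may have arisen at any time in the preceding 52 − 26 = 26 weeks. Study drug runs to that visit (6.1) and no later visit is scheduled (6.1.1), so scheduled off-drug observation is 0 days. Abnormalities found at week 6 or 26 do have later visits, and a participant who stops study drug early is encouraged to stay to the final visit (8.6.2). The gap therefore concerns events still open at completion, not all events.

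**3. Other routes by which data could arrive after week 52.**

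| Route | Where | Does it close the gap? |
|---|---|---|
| UADE follow-up | Protocol 8.2.9 | No, device effects only |
| 780G continued access, adverse events captured about every 3 months | Protocol 3.1.1.2 | Partly, some Medtronic users, for a limited period |
| Pregnancy outcome | Protocol 9.5 | No, different event |
| Reporting clocks for SAEs and other events | Protocol 8.4 | No, these govern reporting, not follow-up to resolution |
| Safety analysis | SAP Section 13 | No, it lists and tabulates what was reported |

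**4. How far continued access reaches.** Cohort A has 98 participants allocated 1:1:1:1, so about 98 × 2/4 = 49 are assigned to HCL. Systems are assigned 1:1 within HCL, so about 49 × 1/2 = 24.5 start on a Medtronic system. The other 98 − 24.5 = 73.5, about 75% of Cohort A, start on Tandem or without HCL and have no equivalent route. Switching between systems is allowed, so this is a planned share, not an exact one.

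**5. Number of children.** About 98 × 2/4 = 49 receive verapamil. The documents give no rate of open drug-related SAEs or EKG/liver events at week 52. At an assumed 1%, 49 × 0.01 = 0.49; at an assumed 5%, 49 × 0.05 = 2.45. The range is about 0.5-2.5 participants, and it rests wholly on the assumed rate.

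**6. The two statements in 8.2.9.** Read literally, the line on ongoing outcomes applies to every AE and SAE without end, while the closing paragraph ends collection for all but UADEs. Read as a general rule followed by a specific end-of-study rule, they are compatible. The text does not say which reading is meant. The closing paragraph also opens with completion or withdrawal, but the cut-off for other events mentions completion only.

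**The case against.** The strongest defence is that this is a deliberate and ordinary limit: a trial has to stop collecting data somewhere, and a specific closing provision may qualify a general one. Much of that defence stands, and it rules out several stronger readings.

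- A reader might infer that 8.2.9 contradicts itself. It does so only on the literal reading. The general-then-specific reading is available, so the wording is unreconciled but not clearly contradictory.
- A reader might infer that these events are closed without an outcome, or that an affected child is abandoned. Neither follows. A code for unresolved events exists, and 8.2.9 says that appropriate medical care should continue. The loss is in the study data.
- A reader might infer that causality cannot be determined. The grounds in 8.2.5 are joined by and/or: timing without another explanation, or a known pattern of response, is enough. The Medical Monitor has the final say (8.2.8). Resolution off drug would add evidence, but its absence does not block the judgement.
- A reader might infer that a week-52 result or cardiology reading that arrives after the visit is discarded. Nothing says so. The tests are scheduled study procedures, and the clocks in 8.4 run from the site becoming aware of the event.
- A reader might apply an event rate to all 98 Cohort A participants, or treat week 52 as a third of the drug-safety information because it is one of three post-screening tests. The 98 include placebo recipients, and a share of scheduled tests is not a share of events or information lost.

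What the defence does not answer is why follow-up after exit, which the protocol already accepts for UADEs, pregnancies and 780G users, leaves out SAEs related to the study drug.

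**Conclusion.** The point holds as a gap in outcome data for drug safety. Under 8.2.9 as written, a study-drug-related SAE, or an EKG or AST/ALT adverse event, that is open when a Cohort A participant completes is left coded as ongoing and its final outcome is not collected, apart from some participants in 780G continued access. What is lost is the evidence on resolution off drug.

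The size is small in numbers: about 0.5-2.5 of roughly 49 verapamil participants if 1-5% have such an event, a rate that is assumed and not taken from the documents. The conclusion itself does not depend on that rate. It rests on the device-only definition of a UADE and on the coincidence of the last dose, last safety tests and last visit. No efficacy result, sample size or power statement is affected. This is a worthwhile, inexpensive improvement, not a flaw that threatens the trial's conclusions.

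**What to change.** Amend the last paragraph of Protocol Section 8.2.9 so that the follow-up rule now reserved for UADEs also covers:

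- SAEs assessed as related to study drug or to a study procedure; and
- EKG or AST/ALT abnormalities reported as adverse events and ongoing at completion, including those identified from the 52-week tests.

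State that this follow-up uses phone contact or usual-care records only. Keep the completion cut-off for all other adverse events, limit the line requiring site follow-up of ongoing outcomes so that it agrees with that cut-off, and say what applies after withdrawal.

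The cost is a short text change plus an occasional call or chart review for a few participants. No new visit, test or study procedure is needed, and no SAP analysis has to change.

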8.3 Reportable Device Issues

All UADES and ADEs as defined in Section 8.2.1 will be reported on both a device issue form and AE form, except for skin reactions from CGM sensor placement or pump infusion set placement that do not require pharmacologic treatment. As noted in Section 8.2.1, events that occur due to participant (user) error generally will not require completion of a device issue form.

Device complaints and device malfunctions will be reported except in the following circumstances. These occurrences are expected and will not be reported on a Device Issue Form assuming criteria for a UADE or ADE have not been met:

- CGM sensor lasting fewer days than expected per manufacturer
- CGM tape adherence issues
- Battery lifespan deficiency due to inadequate charging or extensive wireless communication
- Intermittent device component disconnections/communication failures not requiring system replacement or workaround/resolution not specified in user guide/manual.

1129 • Device issues clearly addressed in the user guide manual that do not require additional
1130 troubleshooting
1131 • Device issues in the non-HCL groups using commercially available Dexcom G6 CGMs if
1132 not associated with an adverse event.

1133 **8.4 Timing of Event Reporting**

1134 Serious AEs that are possibly related to a study device, drug or study participation must be
1135 reported to the Coordinating Center within 24 hours of the site becoming aware of the event.
1136 This can occur via phone or email, or by completion of the online serious adverse event form and
1137 device issue form if applicable. If the form is not initially completed, it should be completed as
1138 soon as possible after there is sufficient information to evaluate the event.

1139 All other reportable ADEs and other reportable AEs should be submitted by completion of an
1140 electronic case report form within 7 days of the site becoming aware of the event.

1141 The Coordinating Center will notify all participating investigators and the IRB of any adverse
1142 event that is serious, related, and unexpected. Notification will be made within 10 working days
1143 after the Coordinating Center becomes aware of the event and no later than seven calendar days
1144 where the event is fatal or life threatening.

1145 Upon receipt of a qualifying event, the Coordinating Center/Medical Monitor will investigate the
1146 event to determine if a UADE is confirmed, and if indicated, report the results of the
1147 investigation to the all overseeing IRBs and the FDA, within 10 working days of the
1148 Coordinating Center becoming aware of the UADE per 21CFR 812.46(b) (2). The Medical
1149 Monitor must determine if the UADE presents an unreasonable risk to participants. If so, the
1150 Coordinating Center must ensure that device use presenting that risk is terminated as soon as
1151 possible but no later than 5 working days after the Medical Monitor makes this determination
1152 and no later than 15 working days after first receipt notice of the UADE.

1153 Device malfunctions will be handled by the Coordinating Center as described below. In the case
1154 of a device malfunction related to a device that is donated to the study by the manufacturer,
1155 information may be forwarded to the manufacturer by the site personnel or the Coordinating
1156 Center.

1157 Each principal investigator is responsible for reporting serious study-related adverse events and
1158 abiding by any other reporting requirements specific to his/her Institutional Review Board or
1159 Ethics Committee. When the JCHR IRB is the overseeing IRB, sites must report all serious,
1160 related adverse events regardless of whether they are expected/anticipated and regardless of
1161 whether they are fatal or life threatening within 7 calendar days. The Coordinating Center will be
1162 responsible for notifying the FDA of any unexpected fatal or life-threatening suspected adverse
1163 reaction as soon as possible, but in no case later than seven calendar days after initial receipt of
1164 the information. In addition, the Coordinating Center will notify FDA and all participating
1165 investigators of potential serious risks, from clinical trials or any other source, as soon as
1166 possible, but in no case later than 15 calendar days after the Sponsor determines that the
1167 information qualifies for reporting.

1173 **8.5 Independent Safety Oversight**

1174 A Data and Safety Monitoring Board (DSMB) will review compiled safety data at periodic
1175 intervals (approximately every 6 months). SAEs, UADES, and any adverse events leading to
1176 study discontinuation will be reviewed immediately by the DSMB. The DSMB also will be
1177 informed of any ADEs not meeting criteria for a UADE if the Medical Monitor requests the
1178 DSMB review. The DSMB can request modifications to the study protocol or suspension or
1179 outright stoppage of the study if deemed necessary based on the totality of safety data available.
1180 Details regarding DSMB review will be documented in a separate DSMB document.

1181 **8.6 Stopping Criteria Related to Study Devices or Drug**

1182 **8.6.1 Participant Discontinuation of Study Device**

1183 In the case of an unanticipated system malfunction resulting in a severe hypoglycemia or DKA
1184 event (or a malfunction that could have led to severe hypoglycemia or DKA), use of the HCL
1185 system will be suspended for all participants while the problem is diagnosed. The UADE will be
1186 reported to the IRB, DSMB, and FDA. After assessment of the problem and any correction, use
1187 of the system will not be restarted until approval is received from the IRB, DSMB, and FDA.

1188 In the absence of a device malfunction, use of the HCL system by a participant will be
1189 discontinued if any of the following occur:

- 1190 • The investigator believes it is unsafe for the participant to continue on the study device
1191 *This could be due to the development of a new medical condition or worsening of an
1192 existing condition; or participant behavior contrary to the indications for use of the
1193 device that imposes on the participant's safety*
- 1194 • The participant requests that the treatment be stopped
- 1195 • Participant has two distinct severe hypoglycemia events as defined in Section 8.2.3
- 1196 • Participant has two distinct episodes of DKA as defined in Section 8.2.4 (not related to
1197 insulin set failure)
- 1198 • Participant pregnancy
 - 1199 • Upon discovery of pregnancy, the use of closed loop will be stopped; however, the
1200 participant may continue use of the study pump and CGM in open loop until an
1201 alternative method for insulin delivery and glucose monitoring is in place. This is to
1202 ensure safety of the participant and unborn child.

1203 Each DKA or severe hypoglycemia event will be reviewed by the Medical Monitor and the
1204 DSMB with respect to determination of cause and whether the occurrence of the event can be
1205 attributed to use of the HCL system.

1206 An additional requirement for continued system use following a single DKA or severe
1207 hypoglycemia event will be that (1) the site investigator believes that the event is explainable,
1208 unlikely to recur, and that it is safe for the participant to continue to use the system and (2) the
1209 Medical Monitor and DSMB concur. If either the Medical Monitor or DSMB determines that the
1210 occurrence of the event indicates that it is not safe for the participant to continue to use the HCL
1211 system, use will be discontinued.

1213

1214
1215 Participants who discontinue a study HCL system will remain in the study (unless the participant
1216 is pregnant, in which case the participant will be dropped from the study). Participants who
1217 discontinue a study HCL system and are not pregnant will remain in the study and be encouraged
1218 to use CGM and an insulin pump, which may be provided by the study.

1219 **8.6.2 Participant Discontinuation of Study Drug**

1220 Rules for discontinuing study drug use are described below.

- 1221 • The investigator believes it is unsafe for the participant to continue to receive the drug.
1222 This could be due to the development of a potential side effect of the drug, a new medical
1223 condition or worsening of an existing condition; or participant behavior contrary to the
1224 indications for use of the drug that imposes on the participant's safety
- 1225 • The participant requests that the treatment be stopped
- 1226 • Participant pregnancy

1227

1228 Even if the study drug is discontinued, the participant will be encouraged to remain in the study
1229 through the final study visit (unless the participant is pregnant, in which case the participant will
1230 be dropped from the study).

1231 **8.6.3 Criteria for Suspending or Stopping Overall Study**

1232 If any UADE occurs, the use of that study device may be suspended or stopped completely,
1233 pending Medical Monitor and DSMB review. If the study device in question is deemed to be
1234 unsafe, any participants currently using that device will be switched to a different HCL system, if
1235 possible. If there is not another FDA approved system, enrollment of the trial as a whole may be
1236 stopped until the issue is resolved.

1237

1238 In addition, study activities could be suspended if the manufacturer of any constituent study
1239 device requires stoppage of device use for safety reasons (e.g., product recall). The affected
1240 study activities may continue if participants can switch to a different FDA approved HCL system
1241 or the underlying problem can be corrected by a protocol or system modification that will not
1242 invalidate the results obtained prior to suspension.

1243

1244 If any death occurs in the study which is assessed as related to study treatment regimen by the
1245 study site investigator and Medical Monitor (but not limited to a specific study device that can be
1246 switched), enrollment in the trial will be halted, pending DSMB review.

1247

1248 As part of their ongoing safety review, the DSMB will make independent judgments regarding
1249 other adverse events that may warrant trial interruption.

1250

1251 The study Medical Monitor will review all adverse events and adverse device events that are
1252 reported during the study typically on a weekly basis and will review compiled safety data at
1253 periodic intervals (generally timed to the review of compiled safety data by the DSMB). The
1254 Medical Monitor may request suspension of study activities or stoppage of the study if deemed
1255 necessary based on the totality of safety data available.

1256

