1082 Medical Monitor's MedDRA coding will be used for all reporting). The Medical Monitor will
1083 review the investigator's assessment of causality and may agree or disagree. Both the
1084 investigator's and Medical Monitor's assessments will be recorded. The Medical Monitor will
1085 have the final say in determining the, expectedness and causality as well as whether an event is
1086 classified as a serious adverse event and/or an unanticipated adverse device effect.

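### The 24-hour reporting rule in Protocol 8.4 leaves out serious events judged unrelated, though 8.5 and 8.6.1 call for prompt DSMB review of them

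*Protocol*

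**What the plan says.** Protocol 8.4 has two clocks from the site to the Coordinating Center.

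- Fast: "Serious AEs that are possibly related to a study device, drug or study participation must be" "reported to the Coordinating Center within 24 hours of the site becoming aware of the event". Phone or email notice is enough.
- Slow: "All other reportable ADEs and other reportable AEs should be submitted by completion of an" "electronic case report form within 7 days of the site becoming aware of the event".

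There is no separate line for SAEs judged unrelated, so by default they take the slow clock.

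Other sections bear on how soon the reviewers need to know:

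- **8.2.3 and 8.2.4** make every SH event and every DKA event an SAE for reporting purposes.
- **8.2.5** has the site investigator rate each event as related or unrelated.
- **8.2.8** lets the Medical Monitor "have the final say in determining the, expectedness and causality as well as whether an event is" an SAE or a UADE.
- **8.5** lists SAEs, UADEs and events behind a discontinuation for prompt DSMB attention, with no limit to related events: "study discontinuation will be reviewed immediately by the DSMB. The DSMB also will be" told of some other device effects.
- **8.6.1** sends each SH and DKA event to the Medical Monitor and the DSMB to decide its cause and whether the HCL system is responsible. It then sets a condition: "An additional requirement for continued system use following a single DKA or severe" hypoglycemia event is that the site investigator considers it safe and that the Medical Monitor and DSMB concur.
- **8.6.1** also covers an unanticipated malfunction that results in an SH or DKA "event (or a malfunction that could have led to severe hypoglycemia or DKA), use of the HCL" system is then suspended for all participants. It calls such a case a UADE.

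**The concern.** The site's provisional opinion on cause decides how quickly the people who must rule on cause hear of the event. The site makes the first relatedness judgment, the Medical Monitor can overrule it, and the DSMB must review the event either way. Yet under 8.4 the judgment that may be overruled is the one that sets the deadline.

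This matters most for SH and DKA in the HCL groups. These are children on systems that are partly investigational, and 8.6.1 makes continued use after one event depend on agreement from reviewers outside the site. A site can meet 8.4 to the letter while those reviewers do not yet know that there is anything to review. Independent review adds most when a site has found a reason to think the device was not involved, and that is when notice may come latest.

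The issue is safety oversight. It does not affect the C-peptide analyses.

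**Working it through.** The plan states no figure to reproduce, so the check sets the sections side by side. The only arithmetic is the difference between the two clocks.

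**Step 1. Which clock applies?**

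| Event | Serious for reporting? | Site's relatedness call (8.2.5) | Latest notice to Coordinating Center (8.4) |
|---|---|---|---|
| SH or DKA | Always (8.2.3, 8.2.4) | Related | 24 hours |
| SH or DKA | Always | Unrelated | 7 days |
| Other SAE | Yes | Related | 24 hours |
| Other SAE | Yes | Unrelated | 7 days |
| HCL malfunction that caused SH or DKA | Yes, through the event | Ordinarily related | 24 hours through the event; the malfunction is not named |
| HCL malfunction that might have caused SH or DKA, with no harm | UADE under 8.6.1 | Not addressed | No explicit fast deadline; 7 days at the latest if the AE form required by 8.3 brings it under 8.4 |

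Section 8.4 does not say who decides possible relatedness at first report. That it is the site follows from 8.2.5.

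**Step 2. Size of the gap.** 24 hours = 1 day, and 7 − 1 = 6 days. An unrelated SAE may be notified up to 6 days later than a related one, and up to 7 days after the site learned of it.

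**Step 3. Do the reviewers' duties have the same limit?**

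| Duty | Limited to related events? |
|---|---|
| Immediate DSMB review of SAEs (8.5) | No |
| Medical Monitor and DSMB review of each SH or DKA event for attribution to HCL (8.6.1) | No; attribution is the question they are asked |
| Their concurrence before continued HCL use after one event (8.6.1) | No |
| Medical Monitor's final decision on causality and seriousness (8.2.8) | No |

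None of the four duties depends on the site's call, but the 24-hour clock does. The Medical Monitor's power to change the causality rating cannot close the gap, because it is exercised on a report already received.

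**Step 4. Other deadlines.** The UADE limits in 8.4 are 10 working days to report the investigation, and 5 and 15 working days to end risky device use. They run from the Coordinating Center's awareness or receipt, or from the Medical Monitor's determination, so none is a deadline for the site. Section 8.1 asks sites to report unanticipated problems promptly but gives no number of days for reaching the Coordinating Center. Its 7 calendar days are for reporting to the IRB by sites under the central IRB.

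**The case against.** The strongest reply is that the gap is narrow. Section 1.2.1 names DKA and SH as potential adverse effects of the HCL system, including through inadequate or erroneous insulin dosing. Section 8.2.5 allows an event to be called related when it follows a known pattern of response. Many HCL-group events may therefore get the 24-hour clock, and 7 days is a ceiling that sites may rarely approach. This stands, and it limits the finding to the events that sites do judge unrelated. It does not remove those events.

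It can also be said that immediate review in 8.5 may run from the DSMB's receipt, and that a separate DSMB document, not available here, holds the details. Both are possible. Neither would change the site deadline in 8.4.

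A reader might draw four stronger conclusions, which the documents do not support.

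- *A near-miss malfunction has no reporting clock and could go unreported indefinitely.* Section 8.6.1 treats it as a UADE, 8.3 puts UADEs on both a device issue form and an AE form, and 8.1 may require prompt reporting. What is missing is an explicit fast deadline for the site.
- *Following 8.4 makes 8.6.1 impossible to carry out, or permits 6 more days of HCL use.* The concurrence rule in 8.6.1 binds whatever the form deadline is, and 8.4 authorizes no device use in the interval.
- *An event put down to a bolus or carbohydrate error will be recorded as unrelated.* The user-error wording in 8.2.1 defines an adverse device effect. Relatedness is judged under 8.2.5, which leaves room for either answer.
- *A 7-day delay after a malfunction exposes about 250 child-days.* That is 71 ÷ 2 = 35.5 children per system × 7 days ≈ 249. It assumes that all 71 planned HCL participants are on study at once. Enrollment was staggered, about 10% dropout was expected, and the Medtronic half is split between two models.

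**Conclusion.** The point holds as an inconsistency between sections that should be corrected. For an SAE the site judges unrelated, including SH and DKA, 8.4 permits notice up to 7 days after site awareness. Sections 8.5, 8.6.1 and 8.2.8 assign review, attribution and concurrence to others regardless of that judgment.

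The size is up to 6 days beyond the 24-hour clock, per affected event. The documents give no basis for estimating how many events would be affected. The Medical Monitor's routine review is typically weekly (8.6.3), which might suggest a total lag near 7 + 7 = 14 days. I do not rely on that, because 8.5 calls for immediate review of SAEs.

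The conclusion rests on two readings: that the site makes the first relatedness call (8.2.5), and that SAEs not possibly related fall among the other reportable events in 8.4. Confidence in the textual gap is high. Its practical effect depends on how sites use the relatedness rating.

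**What to change.** Amend the first sentence of Protocol 8.4 along these lines: all SAEs, including every SH and DKA event whatever the site's view of its cause, and any HCL malfunction that caused or might have caused SH or DKA, are to be notified to the Coordinating Center no later than 24 hours after the site learns of them. Keep 7 days for all other reportable AEs and ADEs. The routine device issues that 8.3 exempts stay exempt.

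Naming the malfunctions closes the lesser gap, since 8.6.1 treats them as UADEs while 8.4 gives them no explicit fast site deadline.

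Sections 8.4, 8.5 and 8.6.1 should be reconciled in the same amendment, including the point from which immediate DSMB review is counted. What happens to HCL use between an event and the reviewers' concurrence is for the sponsor to reconcile; no rule is proposed here.

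The cost is a one-sentence amendment and earlier notice, by phone or email as 8.4 already allows, for a small number of unrelated SAEs and qualifying malfunctions. No data collection or analysis changes.
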